8.6.3 Dispensing of trial product

At all visits, after visit 1, trial product will/can be handed out to the patient or parent/LAR which will cover the patient's need for trial product until the next visit. Trial product can though not be handed out at the end of the trial and at follow-up visits.

A dispensing session must be performed in the IWRS, see section [10](#). See section [9](#) for how the trial product must be stored.

8.6.4 Home treatment training

Home treatment training with injection of turoctocog alfa can start after injections of the first dose at the trial site, and should continue until the patient or parent/LAR is comfortable with the reconstitution and injection process. The training must be documented in the medical records.

A home treatment guide for the reconstitution and injection process must be handed-out to the patient or parent/LAR at every dispensing visit.

If the patient does not follow the planned dosing schedule, the investigator must retrain the patient or parent/LAR if they are performing home treatment.

8.7 Patient compliance

Throughout the trial the investigator will remind the patients to follow the trial procedures and requirements to ensure patient compliance. If a patient is found to be non-compliant, the investigator will remind the patient of the importance of following the instructions given including taking the trial products as prescribed. Full compliance with protocol procedures is expected in this trial. If the investigator concludes that the bleeds a patient experiences are due to exceeded time between doses, the investigator must retrain the patient or caregiver.

Failure of compliance with scheduled visits and trial product injection may result in withdrawal in accordance with the protocol withdrawal criteria, see section [6.4](#).

The investigator must check the patient's compliance by reviewing the diary data to check if the home treatment is administered in the frequency prescribed by the investigator and also if the questions are understood, accurate and complete. Furthermore the investigator must during drug accountability compare the drug consumption in the diary with the number of used vials.

9 Trial product and auxiliaries supplies

Trial supplies comprise trial products and auxiliary supplies. Additional details regarding trial supplies can be found in the Trial Materials Manual (TMM).

NCC 0155-0000-0004, N8, NovoEight[®] and turoctocog alfa are all synonyms of the same trial product. The names are used for different purposes during the development program. NovoEight[®] is the registered trade mark for turoctocog alfa.

Trial products must not be dispensed to any person not included in the trial.

Turoctocog alfa is a formulation for single use and to be reconstituted with 4.3 mL of 0.9% sodium Chloride delivered in prefilled syringes.

After reconstitution the solution appears as a clear or slightly opalescent solution and the solution must not be used if it appears different. In case this happens a technical complaint must be filled in.

9.1 Trial products

The following trial products will be provided by Novo Nordisk, Denmark:

Table 9–1 Trial products

Trial product	Strength	Dosage form	Route of administration
Turoctocog alfa	500 IU/vial	Sterile, freeze-dried powder	Intravenous injection
Turoctocog alfa	2000 IU/vial	Sterile, freeze-dried powder	Intravenous injection
Sodium Chloride	0.9 %, 4.3 mL	Solution for injection in prefilled syringes	Solvent for solution for injection

All sites will be supplied with sufficient trial product on an on-going basis controlled by the IWRS. DUNs will be distributed to the sites according to screening information.

9.1.1 Sodium Chloride (NaCl) for injection

After reconstitution with 4.3 mL Sodium Chloride 0.9%, each vial contains 125 IU/mL of turoctocog alfa (500 IU/vial) or 500 IU/mL (2000 IU/vial). The reconstituted solution must not be further diluted and it is recommended to use turoctocog alfa immediately after reconstitution.

9.2 Labelling and direction for use

Labelling of the trial product will be in accordance with Annex 13²⁰, local regulations and trial requirements.

Detailed instructions regarding reconstitution of turoctocog alfa is described in the TMM and the direction for use (DFU). A DFU which contains details on how to perform the reconstitution of turoctocog alfa must be handed-out to the patient or parent/caregiver at every dispensing visit. The site will be provided with the TMM.

The investigator must document that DFU is given to the patient orally and/or in writing at each dispensing visit.

9.3 Storage

Trial product	Storage conditions ² (not-in-use)	In-use conditions	In-use time ¹
Turoctocog alfa	2-8°C	2-8°C	24 hours
		9-30°C	4 hours
	Below 30°C	N/A	As soon as possible
Sodium Chloride	2-30°C	NA	NA

¹"in-use time" starts from reconstitution is finalised

² Expiry date will be stated on the trial product

At the trial site turoctocog alfa must be stored at 2-8°C, and the patient is requested to store the turoctocog alfa refrigerated. If necessary, the patient may also store the turoctocog alfa up to 30°C, but not longer than 6 months. Please ensure the patient record the date when turoctocog alfa starts to be stored at room temperature on the carton. Do not store turoctocog alfa in the refrigerator again after it has been stored at room temperature.

The investigator must ensure the availability of proper storage conditions, record and evaluate the temperature. The investigator must inform Novo Nordisk immediately if any trial product has been stored outside specified conditions (e.g. outside temperature range).

Trial product that has been stored improperly must not be dispensed to any patient before it has been re-evaluated and approved for further use by Novo Nordisk. The investigator must take appropriate action to ensure correct storage.

9.4 Drug accountability and destruction

Drug accountability is the responsibility of the investigator. The investigator or delegated person will perform drug accountability in the IWRS Drug Accountability module.

The IWRS will allocate all trial products DUN (dispensing unit number) to the patient at each dispensing visit. The correct DUNs according to the dispensing session in IWRS must be dispensed to the patient and recorded in the Drug Accountability module by the investigator or delegated person after they have been handed out to the patient.

Unused trial product must be stored separately from used trial product.

Returned trial product (used/partly used or unused including empty packaging material) can be stored at room temperature and must be stored separately from non-allocated trial product. All returned and lost DUNs (except Sodium Chloride) must be recorded in the Drug Accountability module by the investigator or delegated person.

It will not be possible for sites to perform drug accountability for the solvent syringes, thus no drug accountability will be performed for Sodium Chloride.

Destruction will be done according to local procedures after accountability is finalised and verified by the monitor. Destruction of products must be documented using the IWRS, with the exception of Sodium Chloride.

9.5 Auxiliary supplies

All auxiliaries used in this trial will be provided by Novo Nordisk such as syringes, butterflies and vial adapters etc.

10 Interactive voice/web response system

A trial-specific interactive voice/web response system (IWRS) will be set up which can be accessed at any time via the internet or telephone. Access to the IWRS must be restricted to and controlled by authorised persons.

IWRS is used for:

- Screening
- Screening failure
- Trial product arrival
- Dispensing including dispensing for PK
- Dispensing of additional trial products (including surgery)
- Withdrawal
- Completion
- Drug accountability
- Data change

IWRS user manuals will be provided to each trial site.

11 Adverse events and technical complaints

11.1 Definitions

Adverse event

An AE is any untoward medical occurrence in a patient administered a product, and which does not necessarily have a causal relationship with this treatment.

An AE can therefore be any unfavourable and unintended sign (including an abnormal laboratory finding), symptom or disease temporally associated with the use of a product, whether or not considered related to the product.

An AE includes:

- A clinically significant worsening of a concomitant illness.
- A clinical laboratory adverse event (CLAE): a clinical laboratory abnormality which is clinically significant, i.e. an abnormality that suggests a disease and/or organ toxicity and is of a severity that requires active management. Active management includes active treatment or further investigations, for example change of medicine dose or more frequent follow-up due to the abnormality.

The following should **not** be reported as AEs:

- Pre-existing conditions, including those found as a result of screening procedures (pre-existing conditions should be reported as medical history or concomitant illness).
- Pre-planned procedures unless the condition for which the procedure was planned has worsened from the first trial related activity after the patient has signed the informed consent.
- Disease related bleeds and other symptoms (e.g. pain, swelling, synovitis, arthralgia, injection site haematoma) in connection to bleeds that is evaluated by the investigator as part of the underlying disease should not be reported as AEs or SAEs unless evaluated by the investigator as related to trial product. In case of fatal/life-threatening outcome, the bleeding episode must be reported as a SAE. All bleeds and other symptoms related to the underlying disease will be captured in the medical records or diary.

The following three definitions are used when assessing an AE:

- **Severity assessment**
 - **Mild** - no or transient symptoms, no interference with the patient's daily activities.
 - **Moderate** - marked symptoms, moderate interference with the patient's daily activities.
 - **Severe** - considerable interference with the patient's daily activities; unacceptable.
- **Causality assessment**

The following terms are used when assessing the relationship between an AE and the relevant trial product(s):

- **Probable** - Good reason and sufficient documentation to assume a causal relationship.
- **Possible** - A causal relationship is conceivable and cannot be dismissed.
- **Unlikely** - The event is most likely related to aetiology other than the trial product.

If the patient has been exposed to both vial strengths then causality needs to be rated against both vial strengths.

- **Final outcome of an AE**

- **Recovered/resolved** - The patient has fully recovered, or by medical or surgical treatment the condition has returned to the level observed at the first trial-related activity after the patient signed the informed consent.
- **Recovering/resolving** - The condition is improving and the patient is expected to recover from the event. This term is only applicable if the patient has completed the trial or has died from another AE.
- **Recovered/resolved with sequela** - The patient has recovered from the condition, but with lasting effect due to a disease, injury, treatment or procedure. If a sequela meets an SAE criterion, the AE must be reported as an SAE.
- **Not recovered/not resolved** - The condition of the patient has not improved and the symptoms are unchanged, or the outcome is not known.
- **Fatal** - This term is only applicable if the patient died from a condition related to the reported AE. Outcomes of other reported AEs in a patient before he/she died should be assessed as "recovered/resolved", "recovering/resolving", "recovered/resolved with sequela" or "not recovered/not resolved". An AE with fatal outcome must be reported as an SAE.
- **Unknown** - This term is only applicable if the patient is lost to follow-up.

Serious adverse event

A SAE is an experience that at any dose results in any of the following:

- Death.
- A life-threatening^a experience.
- In-patient hospitalisation^b or prolongation of existing hospitalisation.
- A persistent or significant disability or incapacity^c.
- A congenital anomaly or birth defect.
- Important medical events that may not result in death, be life-threatening^a or require hospitalisation^b may be considered an SAE when - based on appropriate medical judgement - they may jeopardise the patient and may require medical or surgical intervention to prevent one of the outcomes listed in the definition of SAE^d.

- a. The term "life-threatening" in the definition of SAE refers to an event in which the patient was at risk of death at the time of the event. It does not refer to an event which hypothetically might have caused death if it was more severe.
- b. The term "hospitalisation" is used when a patient:
 - Is admitted to a hospital or in-patient, irrespective of the duration of physical stay, or
 - Stays at the hospital for treatment or observation for more than 24 hoursMedical judgement must always be exercised, and when in doubt, the hospital contact should be regarded as a hospitalisation. Hospitalisations for administrative, trial-related and social purposes do not constitute AEs and should therefore not be reported as AEs or SAEs. Hospital admissions for surgical procedures, planned before trial inclusion, are not considered AEs or SAEs.
- c. A substantial disruption of a patient's ability to conduct normal life functions (e.g. following the event or clinical investigation the patient has significant, persistent or permanent change, impairment, damage or disruption in his/her body function or structure, physical activity and/or quality of life).
- d. For example intensive treatment in an emergency room or at home of allergic bronchospasm, blood dyscrasias or convulsions that do not result in hospitalisation, or development of drug dependency or drug abuse.

The following adverse events must always be reported as an SAE using the important medical event criterion if no other seriousness criteria are applicable:

- suspicion of transmission of infectious agents via the trial product
- risk of liver injury defined as alanine aminotransferase (ALT) or aspartate aminotransferase (AST) >3 x UNL and total bilirubin >2 x UNL, where no alternative aetiology exists (Hy's law).
 - inhibitor development confirmed by two consecutive FVIII positive inhibitor tests (≥ 0.6 BU)

Non-serious adverse event

A non-serious AE is any AE which does not fulfil the definition of an SAE.

Medical event of special interest

A medical event of special interest (MESI) is an event which, in the evaluation of safety, has a special focus. A MESI is an AE (SAE or non-serious AE) which fulfils one or more of the below defined MESI criteria.

1. Medication errors concerning trial products:

- Injection of wrong drug or use of wrong device
 - Wrong route of injection, such as intramuscular instead of intravenous
 - Injection of an overdose with the intention to cause harm (e.g. suicide attempt)
 - Accidental injection of a lower or higher dose than intended. The administered dose must deviate from the intended dose to an extent where clinical consequences for the trial patient were likely to happen as judged by the investigator, although not necessarily did happen
2. Inhibitor formation against FVIII
- If an investigator obtains any indication of inhibitor formation by clinical signs or local laboratory results, it must be reported as a MESI
 - Blood samples for measurement of FVIII inhibitors will be analysed at the central laboratory selected by Novo Nordisk and if the first test is positive (≥ 0.6 BU) a MESI must be reported by the investigator
 - A second consecutive FVIII inhibitor test must be performed if the first test is positive – sampled preferably within 2 weeks. The results of the second confirmatory inhibitor test must be reported as follow up to the MESI already reported regardless of the result. In case the patient stays in the trial with a positive inhibitor test, but < 5 BU all subsequent inhibitor test must be reported as follow-up to the SAE
 - In case the patient is withdrawn, and continues with follow-up visits, all the inhibitor tests at these visits must be reported as follow-up to the SAE
3. Allergic reaction including anaphylaxis reaction as defined in [Table 11-1](#).
- Allergic reactions included but not limited to any acute immunoglobulin E (IgE) mediated reaction or delayed type hypersensitivity (clinical signs may include various types of skin rashes) that do not meet the definition of anaphylaxis as described in [Table 11-1](#). All hypersensitivity reactions reported as MESI will be followed up with a hypersensitivity questionnaire

Table 11–1 Definition as per the reference by Sampson et al 2006²¹

Anaphylaxis is highly likely when any one of the following 3 criteria are fulfilled:

Acute onset of an illness (minutes to several hours) with involvement of the skin, mucosal tissue, or both (eg, generalized hives, pruritus or flushing, swollen lips-tongue-uvula) and at least one of the following:

- Respiratory compromise (eg, dyspnea, wheeze-bronchospasm, stridor, reduced PEF, hypoxemia)
- Reduced BP or associated symptoms of end-organ dysfunction (eg, hypotonia [collapse], syncope, incontinence)

2. Two or more of the following that occur rapidly after exposure to a likely allergen for that patient (minutes to several hours):

- Involvement of the skin-mucosal tissue (eg, generalized hives, itch-flush, swollen lips-tongue-uvula)
- Respiratory compromise (eg, dyspnea, wheeze-bronchospasm, stridor, reduced PEF, hypoxemia)
- Reduced BP or associated symptoms (eg, hypotonia [collapse], syncope, incontinence)
- Persistent gastrointestinal symptoms (eg, crampy abdominal pain, vomiting)

3. Reduced BP after exposure to known allergen for that patient (minutes to several hours):

- Infants and children: low systolic BP (age specific) or greater than 30% decrease in systolic BP*
- Adults: systolic BP of less than 90 mm Hg or greater than 30% decrease from that person's baseline Peak expiratory flow (PRG); blood pressure (BP).

*Low systolic blood pressure for children is defined as less than 70 mm Hg from 1 month to 1 year, less than (70 mm Hg + [2 x age]) from 1 to 10 years, and less than 90 mm Hg from 11 to 17 years.

Technical complaint

A technical complaint is any written, electronic, or oral communication that alleges product (medicine or device) defects. The technical complaint may be associated with an AE, but does not concern the AE itself.

Examples of technical complaints:

- The physical or chemical appearance of trial products (e.g. discoloration, particles or contamination)
- All packaging material including labelling

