8.4.2 Antibodies

8.4.2.1 FVIII inhibitors

FVIII inhibitors will be measured at every scheduled visit in the main phase. In the extension phase of the trial, inhibitors will be measured at every assessment visit, i.e. at least twice annually. If there is any suspicion of FVIII inhibitor development FVIII inhibitors must be measured at an unscheduled visit. At visit 1 the inhibitor test will be taken for baseline characteristics and must be used for the assessment of exclusion criteria, see section [6.3](#).

Analysis for FVIII inhibitors will be carried out at a central laboratory using the Nijmegen modified Bethesda assay. A positive inhibitor test is defined as ≥ 0.6 Bethesda Unit (BU).

If FVIII inhibitor development is suspected by increased number of bleeding episodes, bleeding episodes difficult to treat and/or peak and trough levels below expected values, a Nijmegen modified Bethesda test must be performed. In addition, a recovery test must also be performed, because the decrease of recovery may indicate an early signal of inhibitor development. If the result of the modified Bethesda test is positive, another sample must be collected for a confirmatory Nijmegen modified Bethesda assay at an unscheduled visit preferably within 2 weeks and not later than 4 weeks of the first positive test result from central lab. The diagnosis of inhibitor is made if the patient has been tested positive for inhibitors (≥ 0.6 BU) at two consecutive tests at central lab.

If the first FVIII inhibitor test is positive, a lupus anticoagulant (see section [8.5.3.5](#)) must be sampled with the second sampling for a confirmatory FVIII inhibitor test at an unscheduled visit. These samples should preferably be sampled prior to any change of treatment. The dose taken at the confirmatory visit is preferable the same as a prophylaxis dose or at the discretion of the investigator.

Blood sampling for FVIII inhibitor test must be performed after a 48 hours washout period since last dosing with trial product.

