If the second confirmatory test is positive (≥ 0.6 BU), but below or equal to 5 BU the patient has a low titer inhibitor, but can continue in the trial. This may only occur if the investigator evaluates that the patient can be treated with turoctocog alfa within the recommended dosing range for prophylaxis and treatment of bleeds according to section [5.3](#). A trough and recovery test and a FVIII activity tests at 60 and 240 min after dosing (see [Table 8–15](#) and section [8.3.4](#)) must be performed at an unscheduled visit as soon as possible and at every scheduled visit hereafter a FVIII trough and recovery test must be taken in the main phase. In the extension phase a patient with a low titer inhibitor must take an inhibitor, trough and recovery test at the assessment, dispensing and at an unscheduled visits every month.

Table 8–15 Sampling times after a positive confirmatory low titer inhibitor test

Time (Min)	Sample window	Remark
-60	(+55)	FVIII trough
00		Dosing
30	(± 5)	FVIII recovery
60	(± 10)	FVIII activity
240	(± 60)	FVIII activity

A confirmed positive inhibitor is considered to have disappeared if the inhibitor is < 0.6 BU on 2 consecutive inhibitor tests (performed at 2 consecutive visits) and the FVIII recovery is $\geq 66\%$ of expected values.

If the second confirmatory test or any test subsequent to this is above 5 BU then the patients must be withdrawn from the trial, see section 6.4, and the inhibitor must be followed up every month for 3 months at the follow-up visits, see section 8.1.9.

See Figure 8–2 for an inhibitor decision tree.

[figure not shown]

Figure 8–2 Inhibitor decision tree

For storage, handling, dispatch, and disposition of samples analysed for FVIII inhibitors at the central laboratory, please refer to detailed guidance in the laboratory manual.

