Data from central laboratories will be transferred electronically from the laboratory performing the analyses. In cases where data is transferred via non-secure electronic networks, data will be encrypted during transfer.

Both the central and local laboratory will provide all laboratory reports to the investigator for storage at the trial site.

The patient and any biological material obtained from the patient will be identified by patient number and trial identification number. Appropriate measures such as encryption or leaving out certain identifiers will be enforced to protect the identity of patients in all presentations and publications as required by local, regional and national requirements.

15 Computerised systems

Novo Nordisk will capture and process clinical data using computerised systems that are described in Novo Nordisk Standard Operating Procedures and IT architecture documentation. The use and control of these systems are documented.

Investigators working on the trial may use their own electronic systems to capture source data.

16 Statistical considerations

Evaluation of data will be based mainly upon descriptive statistics, i.e. summary tables, listings, and figures. Categorical data will be summarised by frequency tables while continuous data will be summarised by mean, standard deviation, minimum and maximum value.

All efficacy endpoints will be reported only for patients without inhibitors (<0.6 BU) and using bleeds with turoctocog alfa treatment. Base on the full analysis set (FAS), but if a patient develops an inhibitor only the time before the positive inhibitor test will be used to evaluate the efficacy endpoints. The following sensitivity analyses will be performed:

- The annualised bleeding rate will be calculated for both treatment-requiring bleeds and non-treatment requiring bleeds
- The annualised bleeding rate will be calculated excluding data from low titer periods
- Treatment success will be summarised excluding data from low titer periods

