16.1 Sample size calculation

No formal sample size calculations have been performed. A sample size of 60 patients is considered a sufficient number of patients to evaluate safety and efficacy of turoctocog alfa. The results of this study will supplement results from a corresponding study in non-Chinese patients.

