16.3 Primary endpoint

- Haemostatic effect of turoctocog alfa when used for treatment of bleeds, assessed on a four-point scale for haemostatic response (excellent, good, moderate and none) during the main phase (6 months duration per patient).

In addition treatment success will be summarised by counting haemostatic responses rated as good or excellent as success and responses rated as moderate and none as failure. If the haemostatic response is missing, the response will be counted as failure in the primary analysis, but a sensitivity analysis will be performed excluding bleeding episodes with missing response. Treatment success will also be summarised excluding data from low titer periods as a sensitivity analysis to the primary analysis.

The haemostatic effect of turoctocog alfa will also be summarised by the following subgroups: Cause of bleed (Spontaneous, Traumatic, Re-bleed), Site of bleeding (Central nervous system, Haemarthrosis (Joint), Gastrointestinal, Subcutaneous, Muscular or other), Classification of bleeding (Mild/Moderate or Severe)

Analyses and presentations will be made by age groups, type of regimen, trial phase and total.

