## 2 Statistical considerations

Evaluation of data will be based mainly upon descriptive statistics, i.e. summary tables, listings, and figures. Categorical data will be summarised by frequency tables while continuous data will be summarised by mean, standard deviation, minimum and maximum value.

All efficacy endpoints will be reported only for patients without inhibitors (<0.6 BU) and using bleeds with turoctocog alfa treatment. Base on the full analysis set (FAS), but if a patient develops an inhibitor only the time before the positive inhibitor test will be used to evaluate the efficacy endpoints. The following sensitivity analyses will be performed:

- The annualised bleeding rate will be calculated for both treatment-requiring bleeds and non-treatment requiring bleeds
- The annualised bleeding rate will be calculated excluding data from low titer periods
- Treatment success will be summarised excluding data from low titer periods

The main CTR will be written when at least 60 patients have completed the main phase of the trial (completed visit 8 and data is available, including PK data). The patients that have not completed the main phase at the cut off time for the main CTR will also be reported as part of the main phase.

These patients will be included with data until their last scheduled visit prior to the cut-off date. The extension phase data at this time will also be included in the main CTR. The main CTR will present data separately (when relevant) for the above mentioned main and extension phase and this data will also be presented combined.

The primary conclusion will be based on the main CTR and only on the above mentioned main phase data. An updated CTR will be conducted when all patients have completed the extension phase of the trial. The updated CTR will present data separately (when relevant) for the main and extension phase and the combined main and extension phase data. The definition of the main phase will be the same in the main and updated reports. See Figure 16–1.

[figure not shown]

Figure 16-1 in the CTR

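### Bleeds after a positive inhibitor test that are attributed to haemophilia and are not life-threatening have no planned summary, and the low titer sensitivity analyses conflict with the rule that excludes them

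*Protocol*

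**What the plan says.** Protocol section 16 sets the efficacy rule: "if a patient develops an inhibitor only the time before the positive inhibitor test will be used to evaluate the efficacy endpoints". SAP section 2 repeats it, and introduces it with "All efficacy endpoints will be reported only for patients without inhibitors (<0.6 BU"). Section 16.4.1 places the annualised bleeding rate, consumption per bleed and total consumption among the efficacy endpoints, so the rule reaches these as well as haemostatic response.

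The same paragraphs, protocol 16.3 and 16.4.1, and the matching SAP sections also plan sensitivity analyses without the low titer periods, for treatment success and for the bleeding rate. For the primary endpoint the text is: "Treatment success will also be summarised excluding data from low titer periods as a sensitivity analysis to the primary analysis".

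On safety, section 11.1 states that bleeds assessed as part of the underlying disease "should not be reported as AEs or SAEs unless evaluated by the investigator as related to trial product". A fatal or life-threatening bleed must be reported as an SAE. Other disease-related bleeds are kept in the diary or the medical records.

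Section 8.4.2.1 says that after a positive confirmatory test of at most 5 BU "the patient has a low titer inhibitor, but can continue in the trial", if the investigator judges that he can be treated within the protocol's dosing range. The same section names the clinical signs that should prompt a test: "If FVIII inhibitor development is suspected by increased number of bleeding episodes, bleeding episodes difficult to treat".

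**The concern.** Keeping disease-related bleeds out of AE reporting is reasonable as long as they are counted under efficacy. For a patient with an inhibitor the efficacy count stops at the positive test, while the AE exemption carries on. The two rules were written for different purposes, and together they can leave a bleed in neither set of tables.

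The first secondary objective is safety in terms of immunogenicity. By the protocol's own account, more bleeds and bleeds that are hard to treat are how an inhibitor shows itself. If a retained low titer patient bleeds more, or responds less well, the planned tables show that he had an inhibitor but not what followed in bleeding, response or consumption.

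**Working it through.** The plan has no figure to reproduce on this point ("No formal sample size calculations have been performed"). The check is to trace one bleed through the rules, then to size the effect.

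**1. A bleed after the positive test in a retained low titer patient**

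| Investigator's assessment | Efficacy tables (section 16 rule) | AE/SAE tables (section 11.1) |
|---|---|---|
| Related to trial product | Out | In |
| Fatal or life-threatening | Out | In, as SAE |
| Underlying disease, neither of the above, no admission | Out | Out |
| Underlying disease, neither of the above, admitted | Out | Out |

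Admission is a general SAE criterion in 11.1, but it does not lift the bleed exemption. Table 8-6 classes bleeds that need hospitalisation as severe. Section 8.4.2.1 defines when an inhibitor has disappeared, but no text returns the patient's later data to the efficacy analysis.

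**2. The exclusion rule against the sensitivity analyses**

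- If the rule governs, low titer periods are already gone from the main analysis, and an analysis that omits them changes nothing.
- If the main analysis keeps low titer periods, the sensitivity analyses make sense, but the rule in section 16 and SAP section 2 is contradicted. Post-test bleeds are then pooled into the main result.

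On neither reading is the inhibitor-positive period summarised on its own. SAP section 3 reports no change from the protocol, so the SAP does not settle it.

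**3. Which test starts the exclusion**

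The rule refers to a positive test without saying whether it is the first or the confirmatory one. Section 8.4.2.1 allows the confirmatory sample up to 4 weeks after the first positive result. That is 28 days, or 28/154 = 18% of the treated main phase computed below. If the confirmatory test is meant, this interval is all that the sensitivity analyses could remove under the rule.

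**4. Size for one affected patient**

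Inputs: visit 2 to visit 3 is 14 days, then five intervals of 28 days (section 8.1.3). Visit 2 to visit 8 = 14 + 5 × 28 = 154 days. Share removed = (154 − day of positive test)/154.

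- Visit 3, day 14: 140/154 = 91%
- Visit 5, day 70: 84/154 = 55%
- Visit 7, day 126: 28/154 = 18%

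Section 7 allows at most 18 months of extension, and its planned dates leave 6 months between the last visits of the two phases. With 30.44 days per month, the total from first dose is 154 + 18 × 30.44 = 702 days, or 154 + 6 × 30.44 = 337 days. For a positive test on day 14, 42 or 154, the share removed is 98%, 94% or 78% over 702 days, and 96%, 88% or 54% over 337 days. These figures assume that he stays to the end.

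**5. Size for the trial**

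One visit 3 case removes 140/(65 × 154) = 1.4% of planned main-phase follow-up. Of prophylaxis follow-up it is 4.1% with 22 patients on that regimen and 1.7% with 53 (the range in Table 6-1).

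Section 3.2 reports no inhibitors in the 213 previously treated patients of the two completed phase 3 trials. The exact 97.5% upper limit for 0/213 is 1 − 0.025^(1/213) = 1.7%. If that limit carried over, the expected number among 65 would be at most 65 × 0.017 = 1.1. The chance of at least one inhibitor of any kind is 1 − (1 − r)^65: 28% at an assumed r of 0.5% and 48% at 1%. Retained low titer patients are only a subset of these.

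**The case against.** A reader might infer that the clinical harm of an inhibitor appears in no planned efficacy or safety summary. The documents do not support that:

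- A confirmed inhibitor is always an SAE. A first positive test, or clinical signs of an inhibitor, is a medical event of special interest (11.1).
- Section 16.4.2 gives the incidence with an exact one-sided 97.5% upper limit (5.52% for 0 of 65, 8.28% for 1 of 65) and splits the AE/SAE tables by inhibitor status.
- Bleeds before the positive test, including those that prompt it, stay in efficacy.
- Bleeds judged related, fatal or life-threatening are reported. A possible relationship requires only that it is conceivable and cannot be dismissed, so an investigator could well call a bleed caused by an inhibitor related.
- Section 6.4 withdraws patients above 5 BU, low titer patients with significantly reduced recovery who respond poorly, and low titer patients who need surgery. Those with the clearest loss of effect should therefore leave.

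All of this stands, and it limits the point. It does not close the gap. The SAE and the incidence rate record that an inhibitor occurred. Section 11.1 sends later inhibitor tests to SAE follow-up and does not mention bleeds. Splitting AE tables by inhibitor status cannot show bleeds that were never AEs. The relatedness call is left to each investigator without guidance for this situation.

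The sensitivity analyses may also mean that low titer bleeds are in the main result after all. If so, the double exclusion fails for treatment success and the bleeding rate, and what remains is the contradiction and the lack of a separate display.

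**Conclusion.** The point holds in a limited form. Under the stated efficacy rule, a bleed after the positive test in a retained low titer patient enters no planned summary if the investigator attributes it to haemophilia and it is neither fatal nor life-threatening. Separately, the rule and the low titer sensitivity analyses cannot both stand as written, and the test that starts the exclusion is not identified.

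The effect is large within an affected patient (18% to 91% of the treated main phase for a positive test between visit 7 and visit 3) and small for the trial (1.4% of main-phase follow-up for one visit 3 case). Few or no cases are expected. That rests on the earlier trials' experience carrying over to this population and on low titer patients continuing in the trial. It would be going too far to say that the plan hides inhibitors, or that the primary result is materially biased. The change is worth making because immunogenicity is a named objective and the remedy is cheap.

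**What to change.** (a) In section 16 and SAP section 2, reconcile the exclusion rule with the low titer sensitivity analyses so that main and sensitivity analyses differ by design. State whether the first or the confirmatory positive test starts the exclusion, and whether data return once the inhibitor has disappeared.

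(b) In 16.4.2 and the SAP safety section, add a per-patient listing of all diary bleeds from the first positive test onward and, if there are enough cases, a descriptive summary. Show time at risk, cause, site, severity, haemostatic response and IU/kg per bleed, and admission where the records give it.

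(c) The sponsor should clarify how the bleed exemption in 11.1 applies after a confirmed inhibitor. This review does not prescribe the rule, and (a) and (b) do not depend on it.

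Cost: one listing or table, a few sentences, and a slightly less favourable display if an inhibitor occurs. Sections 8.3.1 and 8.3.2 already collect most of the items. Admission is not a listed diary item and may have to come from the medical records.
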